## Background, Rationale and Context

**1.B. Overview.** Iron is a risk factor for diabetes and one of its principal complications, NASH. Extensive studies in rodent models and small clinical trials in humans have demonstrated significant and even curative benefit from iron reduction by blood donation. This proposal is to perform a larger randomized, placebo-controlled trial that will test the hypothesis that this simple, safe, inexpensive, and even socially beneficial approach is generalizable to a larger population of individuals with prediabetes and early T2DM. In addition to the large trial for efficacy, we propose in subcohorts to investigate mechanism (changes in insulin sensitivity vs. secretory capacity) and to monitor indices of NASH more intensively. In the application, I will first review the data linking iron with diabetes and NASH, present our Preliminary Data supporting efficacy of iron reduction for both conditions, and describe the proposed low-risk clinical trial to test our hypothesis. If iron reduction succeeds in improving glycemic control and affecting NASH progression, the study would have great impact: (1) Although

[figure not shown]

[figure not shown]
Fig. 1: Iron regulation. Iron enters the circulation from the gut via the iron exporter ferroportin (FPN). Transferrin (Tf)-bound iron enters cells after endocytosis of the Tf Receptor. In the liver, iron stimulates production of hepcidin that feeds back to downregulate FPN.

this trial will test the “iron hypothesis” only in those in the upper half of normal iron, and even though that is by definition half of all people with diabetes, the data reviewed below in **1.C** indicate that iron confers excess risk across its entire “normal” range, so most people with diabetes could benefit from iron reduction; (2) The animal models suggest that the beneficial effect of iron will be long-lived, but even if it were to be eventually overcome, for example by continued weight gain, delaying disease onset by only a few years would still have immense benefits in terms of healthcare costs and the delay in the burden of complications those individuals would otherwise suffer; (3) Finally, iron is also associated with other chronic diseases such as Alzheimer’s (see below), and the insights gained in this study may be applied to those conditions as well.

**1.C. Iron and the risk for diabetes.** Iron is a required cofactor for fuel oxidation and energy production. The cell’s need for iron in the face of its potential danger as an oxidant has given rise to a complex system, coordinated across tissues, to tightly regulate its levels, distribution, and bioavailability (**Fig. 1**). In yeast, the switch from fermentative (glycolytic) metabolism to oxidative phosphorylation is dependent on the presence of iron in the environment. Conversely iron, a potentially dangerous oxidant, is not imported into the cell unless there is a need for oxidative phosphorylation. Thus, there has arisen over evolution an important link between iron homeostasis and metabolism, and we have shown many of those connections are conserved in humans.

Although iron deficiency is one of the most common nutritional deficiencies in the world, humans can also experience pathologic iron overload in conditions such as hereditary hemochromatosis (HH), where the dangers of excess tissue iron were first appreciated. HH, for example, is associated with diabetes, nonalcoholic steatohepatitis (NASH), and an increased risk of Alzheimer’s disease (1). The crucial fact that iron plays a causal role in HH has been demonstrated by improved insulin secretion (2), and protection from progression of liver disease (3) after phlebotomy to normalize body iron stores. Iron overload resulting from frequent blood transfusions is also associated with diabetes risk, and that risk has decreased since the initiation of aggressive iron chelation therapy in patients with beta thalassemia (4).

Beyond pathologic iron overload, the question has arisen if there is also a relationship between T2DM and tissue iron levels in the broad “normal” range. Epidemiologic evidence demonstrates a clear association between diabetes risk and serum ferritin, a generally reliable biomarker for tissue iron stores. In the NHANES cohort the odds ratios for diabetes in those with elevated serum ferritin levels are 4.9 for men and 3.6 for women (**Fig. 2**, Ford studies) (5). *Importantly, progressively increasing risk is seen through the entire range of normal ferritin* (6). Because ferritin is also a marker of systemic inflammation, these relationships were initially attributed to the inflammation associated with diabetes. Studies have shown, however, *the diabetes risk associated with high iron is not accounted for by HH or inflammation but rather by increased dietary intake* (7). Recent studies of gestational diabetes have shown that the increased risk is associated in particular with intake of heme from red meat, which is more efficiently absorbed than non-heme iron (8). These studies suggest that eating as little as 1.5 pounds of red meat per week can raise iron to the levels that are associated with T2DM.

Similar relationships among iron and T2DM risk, insulin resistance, or both are seen in Europeans and African-Americans (6, 9), gestational DM (8, 10, 11) and prediabetes (12). The relative risk of diabetes as a function of iron/ferritin in key studies is summarized in **Fig. 2**. High ferritin also doubles the risk for metabolic syndrome (MetS), the constellation of impaired glucose tolerance, obesity, hyperlipidemia, and hypertension, after accounting for other risk factors (13). The detrimental effects of high-normal iron on tissue function take on extra importance because of iron’s association with a number of other diseases including NASH (14), Parkinson’s and Alzheimer’s diseases (15), colon/breast cancer (16), and cardiovascular disease (17).

Demonstrated mechanisms for the beneficial effects of lowering iron in “garden variety” T2DM and MetS include improvements in insulin secretion (2) and insulin sensitivity (18, 19), the principal determining factors of T2DM. Increased insulin sensitivity is mediated at least in part by adiponectin, which is directly regulated by iron (20). Proof of a causal role of iron in T2DM, and more importantly its reversibility, have been shown in rodent diabetes models (21) and by relatively small studies in humans that demonstrated improvements in fasting glucose, hemoglobin A1c (HgbA1c), and insulin sensitivity after modest phlebotomy to reduce iron from the upper to the lower ranges of normal (20, 22, 23).

Low iron/ferritin is also a marker for so-called “healthy obesity,” namely obesity that does not proceed (or perhaps has not yet proceeded) to MetS and diabetes. Comparing individuals with BMI >40, some with no evidence of MetS other than waist girth, and others that had all elements of MetS (hypertension, glucose intolerance or diabetes, high serum triglycerides [Tg], and low HDL), we found serum ferritin to be nearly twice as high in the MetS group (20). Possible mechanistic contributors are the regulation of both adiponectin and leptin by iron cited above (20, 24). In rodents, it is also possible to maintain healthy obesity by decreasing bioavailable iron in adipocytes: Mice on the Ob/Ob background with adipocyte-targeted over expression of an iron-sulfur cluster binding protein, MitoNEET, *weigh up to 140 g but do not develop diabetes or NAFLD* (25).

**1.D. Iron and the progression of nonalcoholic fatty liver disease (NAFLD).** NAFLD, a condition that has been termed the hepatic manifestation of MetS and T2DM, is present in a majority of people with T2DM and is becoming the most common reason for liver transplantation. Many pathways contribute to NAFLD, but just as all obesity does not proceed to diabetes, not all NAFLD proceeds to NASH, and excess tissue iron is shared as a risk factor for both progressions (see above and (14, 26)). A link between iron and the progression of NAFLD to NASH has also been noted in genome wide association studies wherein increased risk of NASH is seen in individuals with mutations in the genes that cause thalassemia and HH, both of which result in iron overload (27). NAFLD and/or NASH are also associated with polymorphisms in genes connected to pathways that we have shown to be iron-regulated, including leptin, adiponectin, and PPAR $\gamma$  coactivator 1  $\alpha$  (PGC1 $\alpha$ ) (28). In these cases, the effect of the polymorphisms that confer diabetes risk is the same as that of high iron, namely decreased pathway activity (Preliminary Data and (28)). This congruence of genetic underpinnings of NAFLD/NASH with the effects of iron validates many of the linkage that we propose to test.

[figure not shown]
The issue of the causality of the relationship between elevated serum ferritin and increased risk for progression to NASH is as germane to this disease as to diabetes. NASH is by definition an inflammatory disorder that could increase ferritin by that mechanism and confound the relation of iron to the disease. However, large studies have demonstrated *in biopsy-proven NAFLD/NASH that ferritin is more closely related to liver iron*

content than to markers of inflammation (29).

Most importantly, proof of causality rests on interventional studies that demonstrate improvement or delayed progression of disease with iron reduction. Reducing iron by phlebotomy or chelation in humans has been shown to improve NAFLD/NASH (29-31). Other studies are conflicting, but they have employed a wide range of thresholds and targets for tissue iron and differing inclusion criteria, and suffer from underpowering and differing time windows of analysis after iron reduction. A recent meta-analysis concluded there was no benefit to NASH of iron reduction by phlebotomy (32). At odds with that conclusion, that very same analysis did reveal that phlebotomy results in a significant reduction in the canonical marker of NASH, the serum transaminase ALT. Furthermore, the two most prominent “negative” studies in that analysis were one in which the pre-treatment population started with *normal* transaminases (hence, not showing improvement was a foregone conclusion) and the other followed subjects with NASH for only 6 months, a time that had been previously shown in a positive study to be insufficient to demonstrate improvement (33). Thus, based at least in part on a seriously flawed analysis, phlebotomy (or blood donation), which is a safe, simple, acceptable and promising therapy, has not been widely adopted. Even if it were, thresholds for initiating phlebotomy, optimal targets for iron levels, the best rates to achieve those targets, and the longevity of the effects are not known. Furthermore, we have an incomplete understanding of all the pathways impacted by iron modulation. Thus, our laboratory has continued to study the basic science of iron and metabolism even while also pursuing funding for clinical trials.

[figure not shown]
**1.E. Preliminary Data: Phlebotomy for prediabetes and T2DM).** To demonstrate the benefits of reducing iron on glucose homeostasis, we recently completed a pilot study in which subjects (N=11, 9M and 2F, aged  $57.2 \pm 1.2$  yr, BMI  $30.6 \pm 2$  kg/m^2) with prediabetes (N=3) or early T2DM (N=8) were treated with phlebotomy in order to reduce serum ferritin concentrations. No subjects had evidence of systemic inflammation as assessed by medical history or elevated C-reactive protein. Individuals treated with phlebotomy achieved a significantly lower serum ferritin level with biweekly to monthly 1 Unit donations (average  $3.4 \pm 0.5$  Units, or  $\sim 1.7$  L) of blood, providing further evidence that the elevations in ferritin were related to iron and not inflammation. Women started with lower ferritin ( $92 \pm 2$  ng/mL) compared to men ( $219 \pm 32$  ng/mL,  $p < 0.04$ ) and thus achieved less absolute lowering of their ferritin ( $56 \pm 7$  ng/mL) than did the men ( $150 \pm 33$  ng/mL). Average weights increased slightly but not significantly in both groups over the course of the study (1.8 kg in treated, 3.1 kg in controls,  $p = \text{NS}$ ). Blood hemoglobin concentrations tended to decrease in the treated group ( $p = 0.10$ ); only one subject declined to below the normal range (by 0.1 g/dL, less than 1% below normal) and recovered to normal by the end of the study. There were no serious adverse events and no fainting.

**Improved glucose tolerance after phlebotomy.** Phlebotomy treatment resulted in significant lowering of

area under the glucose curve (AUCg) during a 120 min oral glucose tolerance test (average improvement  $1340 \pm 570$  [mg/dL]\*min,  $p < 0.05$  by paired t test). Non-treated controls increased their AUCg value by an average of  $1110 \pm 670$  (mg/dL)\*min, significantly different from the treated group (Fig. 3,  $p < 0.04$ ). The decrement in the AUCg after phlebotomy tended to be correlated with the starting AUCg value ( $r = 0.667$ ,  $p = 0.13$ ) and the starting ferritin value ( $r = 0.641$ ,  $p = 0.063$ ). AUCg values also trended to decrease more in those with prediabetes than diabetes ( $-10.3 \pm 2.2\%$  compared to  $-2.9 \pm 2.3\%$ ,  $p = 0.06$ ), suggesting that early intervention, perhaps before critical loss of beta cell mass, will prove to have the greater beneficial effect.

**Disposition index determined by frequently sampled intravenous glucose tolerance test (FSIGTT) is improved by phlebotomy.** A subset of the subjects (1 control, 8 treated) underwent FSIGTT before and after iron reduction. The disposition index (DI), which is the product of the values for insulin sensitivity ( $S_i$ ) and acute insulin response to glucose (AIRg), serves as a better predictor of diabetes risk than either  $S_i$  or AIRg alone (34). Among the treated subjects, DI improved in seven of eight ( $P < 0.04$  for the entire group, by paired t test). The single control subject undergoing FSIGTT experienced a 72% worsening in DI over the study period. Among all of the subjects, the increase in DI (log transformed) was significantly correlated to the change in ferritin during the study (Fig. 4,  $p < 0.04$ ). The reasons for the improvement in DI varied. Every treated subject improved in terms either of insulin secretion (N=6 of 9, average increase in those 6 of 23.7%,  $p = \text{NS}$ ), insulin sensitivity (N=6 of 9, average increase in those 6 of 51.9%,  $p = \text{NS}$ ), or both (N=3 of 9).

In this small study sample, there was a hint that iron reduction to the very lower limit of normal was not optimally beneficial, and a recent epidemiologic study has suggested a possible optimal ferritin level in the range

of ~40-60 for men and ~30-50 for women, values that are in the 2nd lowest decile of normal.

[figure not shown]

Fig 5. (A) Liver TNF $\alpha$  mRNA, (B) serum ALT, and (C) liver collagen 1 $\alpha$  mRNA in mice fed the

**Improvement in indices of NASH with reduced dietary iron intake.** We have demonstrated in a mouse model that a low iron diet protects from NASH (**Fig. 5**). Mice were fed a “fast food” (FF) diet (~30% fat and fructose-supplemented water) that had previously been shown to result in obesity, insulin resistance, and hepatic inflammation. We varied the iron content from low (4 mg iron/kg chow, but not resulting in iron-deficient insofar as animals maintain normal blood Hgb) to a level seen in some normal chow (35 mg/kg) to a high level (2000 mg/kg, resulting in tissue iron seen in the high end of normal humans). We measured mRNA for TNF  $\alpha$ , an inflammatory cytokine thought to play a role in NASH pathogenesis (**Fig. 5A**), the canonical serum marker of NASH, ALT (**Fig. 5B**), and mRNA for the fibrotic protein collagen 1 $\alpha$  (**Fig. 5C**). In mice fed the FF diet, all three markers increased, but only in the mice on the higher iron diets. The intermediate iron diet also resulted in a delay in the rise of ALT measured at earlier times (not shown).

We also have demonstrated in humans that reduction of iron in individuals with NAFLD/NASH is associated with improvement hepatic inflammation (serum transaminases, **Table 1**, unpublished) and other markers of metabolic syndrome including HgbA1C and lipids (not shown).

	Pre-phlebotomy	Post-phlebotomy
Serum ferritin	398±319 (ng/mL)	47±52*
ALT	64±46 (IU/L)	36±19*
AST	41±26 (IU/L)	28±12*

**Table 1:** Individuals (N=40) with elevated ferritin and a diagnosis of NAFLD or NASH received phlebotomy to lower ferritin to 50 ng/mL. \*p<0.005.

**OBJECTIVES.** Based on the rationale and preliminary data presented, we hypothesize that tissue iron levels in the higher range of normal confer excess risk of T2DM and another common complication of diabetes, NASH. We also hypothesize that this risk is reversible, and markers of both diabetes and NASH will improve and/or progress less in individuals who undergo iron reduction by phlebotomy (blood

donation), sufficient to decrease the biomarker of tissue iron, serum ferritin, from the upper half of normal to the two lowest deciles of normal. The study is an extension of that which resulted in our pilot data, and is aimed at testing our hypothesis in a larger cohort that will provide data on appropriate target populations and threshold and target levels of iron for treatment. Because of the ease, safety, and acceptability of the treatment that would also carry with it an independent societal benefit to blood banks, we believe that this proposed trial could have a major impact on diabetes, NASH, and ultimately other conditions associated with excess nutrition and aging.

## METHODS AND MEASURES

**DESIGN:** We propose a randomized, placebo-controlled trial to determine if reducing tissue iron stores by phlebotomy (blood donation) will improve measures of glycemia in Type 2 Diabetes (T2DM) or prediabetes. Adult subjects (N=240 total) aged 40-75, half with prediabetes and half with early T2DM (controlled by diet or up to 2 nonhypoglycemic agents) with ferritin values in the upper half of normal will be randomized to receive real or sham phlebotomy (blood donation), performed in the same manner as at Red Cross donation centers. Glycemia will be assessed by HgbA1C (primary endpoint), fasting glucose, and continuous glucose monitoring (CGM) before and after treatment. Glycemic outcomes will be assessed 6 and 12 months after achieving the target ferritin. The primary endpoint for which this study aim is powered is a change in HgbA1C at 6 months. As secondary outcomes, we will determine if that improvement is stable over a year, and if there are changes associated with iron reduction in serum alanine transaminase (index of NASH), insulin sensitivity by homeostasis model assessment (HOMA-IR), weight, lipids, blood pressure, changes in the number of diabetes medications for participants with diabetes, and changes in glycemic status (normal, prediabetes or diabetes) for participants with prediabetes. We will also correlate the degree of change in glycemia with the starting ferritin levels and the overall change in ferritin to determine targets and thresholds for iron reduction.

There will be two optional sub studies that will be conducted only at Wake Forest Baptist Medical Center. One will look more closely at liver complications of diabetes and the other will explore whether improvements in glucose levels are due to more insulin production or improved insulin action.

Iron may also play a role in the progression of fatty liver to scarring and cirrhosis. Since 75% of people with diabetes have some degree of fatty liver, we would also like to study how your liver reacts to the lowering of iron.

This will require some additional test, namely an MRI and a liver Ultrasound (Fibroscan). There will be approximately 40 people recruited at Wake Forest Baptist Medical Center for the liver sub study.

The Glucose Tolerance Mechanism substudy will look at the mechanism that your body uses to regulate blood sugar levels by insulin, this will require the frequently sample intravenous glucose tolerance test (FSIVGTT). There will be approximately 48 people recruited at Wake Forest Baptist Medical Center.

**SETTING:** The trial will be performed in two academic health care centers, Wake Forest School of Medicine and Baptist Health Center, and the University of North Carolina at Chapel Hill. Study procedures and intervention will take place in those two institutions' Clinical Research Units supported by their NIH Clinical and Translational Science Awards. At UNC, non-phlebotomy visits may occur at the Eastowne Clinical Research Unit for ease of parking and access.

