- **Sample Size.** In our pilot study of the effects of phlebotomy, we did not measure HgbA1C, but did perform glucose tolerance testing where the difference in area under the curve from pre- to post-treatment was  $1130 \pm 1970$  mg-min/dl. Assuming this average change would be maintained through the day, and converting this change to the relative change in HgbA1C, the change would be expected to be a decrease of ~0.6% (in A1C units, not a change of 0.6% magnitude). With the variance observed, this means a sample size of 32 patients in each group will provide 80% power to detect a difference between the beginning and final HgbA1C in either treatment group at  $p < 0.05$  when pre- and post-phlebotomy results are compared within subjects. This agrees with the published results from another group that did measure HgbA1C, wherein they achieved a significant change ( $p < 0.001$ ) with an N of 31, but a shorter observation period and much less reduction in ferritin. A larger sample size (60/group, 240 total in Aim 1, half diabetes and half prediabetes, with

120 each being randomized to control and phlebotomy) will be recruited to facilitate possible subgroup analysis (e.g. stratification by age, treatment, race, sex) and to allow an up to 20% dropout rate, which is significantly higher than the experience of previous similar studies at Wake Forest University, wherein the dropout rates were in the 12-15% range. (In our pilot study, there were no dropouts.) Thus, we will be theoretically powered to analyze each target ferritin group separately, although the initial analysis will pool the two treatment groups.

- **Multisite study.** This is a multisite study, coordinated by WFUHS, and equal numbers will be recruited at each site, 120 at WFUHS and 120 at UNC Chapel Hill. The Liver substudy will recruit 40 people and the Glucose Tolerance Mechanism substudy will recruit 48 people. The sub studies will be conducted only at Wake Forest Baptist Medical Center.

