### **Outcome Measure(s)**

The primary endpoint will be an improvement in glycemia as assessed by HgbA1C at the first end of study visit, 6 months after phlebotomy. Acutely, HgbA1C will be lowered by blood donation, because that test measures the lifetime exposure of a red blood cell (RBC) to glucose; phlebotomy will result in new RBC synthesis and hence younger RBC, but that effect should disappear soon after the normal RBC lifespan of ~3.5 to 4 months, well before the first post-treatment assessment at 6 months.

A secondary endpoint will be HgbA1C at 12 months to probe longevity of the effect. Based on animal data, we expect that value to be further improved relative to 6 months, but we have no human data on which to support that hypothesis. We do not anticipate that the effect will decline over that time based on reaccumulation of iron. This is a slow process: In individuals with hemochromatosis, for example, iron overload and its adverse effects may not appear until the 5th or 6th decades. In fact, we even anticipate continued improvement as the high levels of tissue iron redistribute and re-equilibrate as processes triggered by decreasing iron proceed, such as autophagy of ferritin complexes, and unloading of macrophages in the face of low hepcidin (Fig. 1).

Fasting glucose will also be assessed at 6 and 12 months after phlebotomy, with secondary endpoints being an improvement at 6 and 12 months. CGM will also be performed using the Abbott Freestyle Libre Pro system for 7-14 days to enhance validation of HgbA1C measures; it allows determination of multiple fasting levels, daily average glucose and various indices of glucose excursions, e.g. postprandial maxima and areas under the curve.

Other secondary endpoints include improvement in insulin sensitivity (decreased HOMA-IR calculated from fasting glucose and insulin), discontinuation of oral antihyperglycemic agents because of improved HgbA1C, change in ALT, changes in weight or blood pressure, and conversion from prediabetes (HgbA1C criteria) to either diabetes or normal glucose tolerance. The secondary endpoints were chosen because they are inexpensive and frequently assessed as part of usual clinical care, and because of the literature suggesting that they are also improved by phlebotomy. Outcomes will also be analyzed using initial, final, and change in ferritin as a continuous variable to interrogate possible optimal thresholds and targets for therapy.

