### **Analytical Plan**

#### **Statistical Plan and Data Analysis.**

The primary analysis will be an analysis of covariance to compare the mean change in the primary endpoint for each aim (HgbA1C at 6 months after phlebotomy for Aim 1, serum ALT at 12 months after phlebotomy for Aim 2, and DI at 6 months after phlebotomy for Aim 3) between the iron depletion and control groups in the full cohort of patients after controlling for the baseline levels of those measurements. The baseline HgbA1C is included as a covariate to increase study power by accounting for regression to the mean between the two time points.

*Secondary Analyses.* The effects of iron depletion on secondary continuous outcomes will be evaluated using analysis of covariance with adjustment for the baseline level of the factor being analyzed as well as the baseline HgbA1C level. For example, we will determine the degree of response (e.g. change in average glucose by CGM) as a function of starting ferritin, ending ferritin, and change in ferritin for determination of dose-response relationships. Treatment effects on dichotomous outcomes (e.g., conversion of pre-diabetes to diabetes) will be evaluated by exact logistic regression, controlling again for the baseline level of the analyzed factor. Ordinal logistic regression will be applied to compare categorical variables with more than 2 ordered categories. In expanded models, interaction terms between the treatment assignment and baseline HgbA1C level will be added to evaluate if the treatment effect differs across the HgbA1C range, and, in particular, between the diabetic and pre-diabetic patients in the study.

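### The plan promises to determine whether the 6-month HgbA1C improvement lasts to a year, but its 12-month analysis never compares the 12-month effect with the 6-month effect

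*Combined protocol and SAP*

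**What the plan says.** The DESIGN paragraph sets the question: "As secondary outcomes, we will determine if that improvement is stable over a year". The Outcome Measure(s) section makes the later value an endpoint: "A secondary endpoint will be HgbA1C at 12 months to probe longevity of the effect". It predicts that the 12-month value will be better than the 6-month value, while admitting that no human data support this, and adds: "We do not anticipate that the effect will decline over that time based on reaccumulation of iron". These are all statements about how the effect changes between two visits.

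The Statistical Plan and Data Analysis section gives secondary continuous outcomes one method: "The effects of iron depletion on secondary continuous outcomes will be evaluated using analysis of covariance with adjustment for the baseline level" (and for baseline HgbA1C). For HgbA1C at 12 months, this estimates and tests the difference between arms at that visit.

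Two other analyses could involve the 12-month data. One is a dose-response analysis: "Outcomes will also be analyzed using initial, final, and change in ferritin as a continuous variable". The other is an interaction of treatment with baseline HgbA1C. Nothing in the document defines stability, sets a margin or retained fraction, contrasts 12 with 6 months, or specifies an arm-by-visit term. The study procedures table shows HgbA1C drawn at both end-of-study visits, so the data for such a contrast will exist.

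**The concern.** A durability question asks whether the treatment effect at 12 months equals, exceeds or falls short of the effect at 6 months. The planned ANCOVA has a different null hypothesis, that there is no arm difference at 12 months. A significant result shows that some effect remains and leaves open how much has been lost. A non-significant result does not show loss, because a small effect that was fully retained can also miss significance.

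What is at stake is a stated secondary objective. The Background overview counts long-lived benefit among the reasons the trial matters. Without a matching analysis or criterion, what counts as stable is left to be decided after the results are known.

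**Working it through.** **Inputs from the plan.** Expected effect: "the change would be expected to be a decrease of ~0.6" points (Sample Size). Pilot change in glucose AUC: 1130 ± 1970 mg-min/dl, with 1970 read as an SD because the plan uses it as the variance for its sample size. Arms: 120 each, with up to 20% dropout, so 120 × 0.8 = 96 per arm. Significance level 0.05, taken as two-sided because the plan does not say.

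**Assumptions not in the plan.** A smaller residual SD of 0.7, shown as an alternative. A 6-to-12-month correlation r of 0.5 to 0.8. The same SD at both visits. Differential dropout and medication changes between visits are ignored.

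**Step 1. The plan's own figure.** It states that "a sample size of 32 patients in each group will provide 80% power to detect a difference between the beginning and final HgbA1C". The paired formula is n = ((1.96 + 0.84) × 1970/1130)² = (2.80 × 1.743)² ≈ 24, or 26 with the t distribution. The stated 32 is not reproduced at 80% power. It matches 90% power by the normal formula: ((1.96 + 1.28) × 1.743)² ≈ 32. The stated figure is therefore conservative. It concerns the 6-month within-subject change and does not bear on this point.

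**Step 2. Implied SD.** 0.6 × 1970/1130 = 1.05 HgbA1C points.

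**Step 3. How the planned 12-month test behaves.** SE = SD × √(2/n). Power ≈ Φ(effect/SE − 1.96).

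At SD 1.05 and 96 per arm, SE = 1.05 × √(2/96) = 0.152. The smallest significant difference is 1.96 × 0.152 = 0.30. A halved effect sits on that threshold, so the test is close to a coin toss. At SD 0.7, SE = 0.101 and power for 0.3 is Φ(2.97 − 1.96) = 84%.

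| True 12-month effect | SD 1.05, n = 96 | SD 1.05, n = 120 | SD 0.7, n = 96 | SD 0.7, n = 120 |
|---|---|---|---|---|
| 0.6 (fully kept) | 98% | 99% | >99% | >99% |
| 0.3 (halved) | about 50% | 60% | 84% | 91% |
| 0.2 (one third) | 26% | 32% | 51% | 60% |

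Among trials already significant at 6 months, the halved effect at SD 1.05 is significant at 12 months in 52% (96 per arm) or 61% (120 per arm). The 0.3 row also applies to a 0.3-point effect that was fully retained. The test responds to the size of the 12-month effect and not to its change.

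**Step 4. What a direct contrast would give.** For (12-month effect − 6-month effect), SE = SD × √(2(1 − r)) × √(2/n). With SD 1.05 and 96 per arm:

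- r = 0.8: SD of change 0.66, 95% half-width 1.96 × 0.66 × 0.144 = 0.19.
- r = 0.5: SD of change 1.05, 95% half-width 1.96 × 1.05 × 0.144 = 0.30.

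If the effect truly fell from 0.6 to 0.3, this interval would exclude zero in about 51% (r = 0.5), 73% (r = 0.7) or 88% (r = 0.8) of trials.

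**The case against.** The strongest reply is that the plan contains no rule turning a significant 12-month difference into a claim of stability. ANCOVA yields an adjusted estimate at each visit, and 0.6 followed by 0.3 would be visible to any reader. A reader might infer that a halved effect would usually be reported as stable. The documents do not support that. They do not say how the 12-month result will be read, and at the only SD derivable from them the halved effect is significant about half the time. The higher figures need a residual SD that the plan does not give. This part of the reply stands. However, two estimates side by side carry no interval for their difference, because they come from the same people and separate ANCOVAs do not supply their covariance.

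It can also be said that the matter is minor: "The primary endpoint for which this study aim is powered is a change in HgbA1C at 6 months", the 12-month wording is exploratory, no hierarchy of secondary outcomes is stated, and fasting glucose and CGM at both visits give further evidence. This limits the importance of the point, and the primary conclusion is untouched. It does not supply the missing comparison. The ferritin models and the baseline-HgbA1C interaction ask who responds and by how much, not whether the effect changed over time.

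A reader might also infer that the plan needs a pass/fail rule, such as requiring the lower 95% bound of (12-month effect − half the 6-month effect) to exceed zero. The documents give no source for that margin, and the rule performs poorly. At SD 1.05, 96 per arm and r of 0.6 to 0.8, it has only 23–31% power for a fully retained 0.3-point effect, against about 50% for the planned test. It would also declare stability in 82–93% of trials when the true effects are 0.1 then 0.4, although the 6-month test would then be significant in only about 10%.

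**Conclusion.** The point holds as a mismatch between question and method. The trial undertakes to determine durability, and no planned analysis compares the 12-month effect with the 6-month effect. The planned test gives a significant result for a halved effect in about 50% of trials at SD 1.05 with 96 per arm, and in 84% at an assumed SD of 0.7. A significant result therefore cannot show that the effect was maintained, and a non-significant one cannot show that it was lost.

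The size depends on the SD. The figure of 1.05 is rescaled from pilot glucose-tolerance data and describes a within-subject change. Baseline adjustment may lower it, but the plan does not say by how much. The mismatch itself does not depend on any SD. The finding does not extend to a prediction of how the investigators will report the result, or to a claim that a stated error rate is exceeded, since the plan states none for durability.

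**What to change.** In the Statistical Plan and Data Analysis section, keep the 6-month arm contrast as primary and add a durability analysis:

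- Analyse HgbA1C at the first and second end-of-study visits together in a repeated-measures model with arm, visit, arm × visit, baseline HgbA1C × visit, and an unstructured covariance.
- Report the 12-minus-6-month change in the treatment effect with its 95% CI as the durability result, interpreted only beside the 6-month effect estimate.
- Use the 12-month ANCOVA only as evidence that an effect is present at 12 months.
- If a stability claim is wanted, the sponsor should choose and pre-specify a retention margin. Otherwise, label durability as an estimate and not a pass/fail claim.

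The cost is plan wording and one extra model, with no new visits, samples or participants. The downside is that the interval may be wide enough (about ±0.19 to ±0.30 points at SD 1.05) to leave durability unresolved.
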